10.3 Analysis of the primary endpoint

Residual volume at first flow-stop, will be analysed in a linear mixed model (LMM) with subjects included as a random component. Evidence of superior effect will be concluded, if the 95% confidence interval of the difference between comparator and investigational device, does not include zero.

The model will include following fixed effects.

- Visit (visit 2 and 3 of catheterisation)
- Device (comparator and investigational device)

The primary endpoint will be evaluated with the null hypothesis being rejected at a 5% significance level (alpha 0.05).

Analysis of sensitivity

- The primary analysis will furthermore be analysed in the PP population, where subjects have received treatment as per protocol.

- Also, a Wilcoxon signed rank test will be applied the primary analysis, under the assumption of data not being normally distributed.

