10.2 Definition of analysis populations

Screening Failures (SF), Intention to Treat (ITT), Full Analysis Set (FAS), Safety and Per Protocol (PP) analysis set will be defined at a formal data review meeting prior to database lock. As a minimum, the data manager, the clinical manager, and the statistician will be involved in the classification of subjects.

Subjects not adhering to inclusion and/or exclusion criteria are considered screening failures (SF) and are not included and randomised.

- The Safety population will constitute all subjects included i.e. subjects who have given informed consent and fulfils the in- and/or exclusion criteria.
- The ITT population will constitute all randomised subjects.
- The full analysis set is a modified ITT population i.e., a sub-population of the ITT population, and will constitute all randomised subjects, who have been exposed to at least one device, with at least one endpoint recorded (data non-missing).
- The PP is a sub-population of the full analysis set where all subjects have received treatment as per protocol.

Individual endpoints/data points may be excluded from the analysis, even though the corresponding subject belongs to any of the pre-defined populations. Exclusion of subjects or data points must be documented.

All statistical analysis and test of hypothesis will be based on the full analysis set, and in addition, primary endpoint will also be analysed in the PP population, whereas adverse events and device deficiencies will be assessed in the safety population.

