10.7 Sample size

Input for the sample size calculations i.e., means and standard deviations are based on three exploratory studies CP322, CP323 and CP324. The studies investigated earlier prototypes of the micro-hole catheter with identical or similar endpoints in populations of both IC users and healthy volunteers.

A sample size for the primary endpoint of residual urine at 1st flow-stop (RV1) is judged to be accommodated by 60 subjects with a power of ~ 90%, assuming a difference of 15 mL, a $sd_{comparator}$ of 50 mL and a sd_{active} of 15 mL (please see Table 3).

Table 3. Sample size calculation of Residual urine at 1st flow-stop in a cross-over design, solving for varying power and number of subjects, assuming no within subject correlation as a worst-case approach, using proc Power in SAS.

μ (sd) comparator	μ (sd) active	Alpha	Power	Sample size
25 (50)	10 (15)	0.05	71.9 %	40
25 (50)	10 (15)	0.05	81.2 %	50
25 (50)	10 (15)	0.05	87.7 %	60
25 (50)	10 (15)	0.05	92.2 %	70

Taken into consideration a discontinuation of 20%, the endpoint of RV1 is sufficiently supported by randomising at least 72 subjects.

If the number of subjects contributing to the primary analysis is less than 60 subjects, it must be carefully considered to include additional subjects (subjects replaced), to maintain sufficient power in the primary analysis.

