10.8 Level of significance and power

A significance level of alpha 0.05 (2-sided) will be applied.

The power for concluding superiority of the investigational device is at least 90% or higher.

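### The primary mixed model states no residual covariance structure. With one common variance and the planned SDs of 50 and 15 mL, the 95% CI has a modestly wrong width if subjects with only a Visit 2 value are uneven between sequences.

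*Combined protocol and SAP*

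**What the plan says.** - **Model (10.3).** The primary endpoint "will be analysed in a linear mixed model (LMM) with subjects included as a random component". The fixed effects are visit (2 and 3) and device (two levels). No residual covariance structure and no degrees-of-freedom method are given.
- **Decision rule (10.3, 10.8).** Superiority is concluded "if the 95% confidence interval of the difference between comparator and investigational device, does not include zero". The level is two-sided: "A significance level of alpha 0.05 (2-sided) will be applied".
- **Planning SDs (10.7).** The calculation is made "assuming a difference of 15 mL", with a comparator SD "of 50 mL and a sd_{active} of 15 mL" and zero within-subject correlation.
- **Discontinuation (10.7).** The 72 randomised subjects are justified by the words "Taken into consideration a discontinuation of 20" per cent. Neither the timing of the losses nor their split between sequences is described.
- **Analysis set (10.2).** The full analysis set, on which the primary test is run, takes randomised subjects "who have been exposed to at least one device, with at least one endpoint recorded (data non-missing").
- **Timing (5.1).** The first product is measured at Visit 2 and the second at Visit 3. A subject who leaves after Visit 2 therefore stays in the primary model with a single value, on one device only.

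**The concern.** A random subject effect plus one residual variance gives both devices the same total variance. The plan's own figures are 50² = 2500 and 15² = 225, a ratio of about 11 to 1.

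A subject with both values enters through the within-subject difference, and that difference has the same variance in either sequence. Pooling does no harm there. A subject with only a Visit 2 value is different: the pooled variance is too small for a comparator value and too large for an investigational one.

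If such subjects are equally frequent in both sequences, the errors cancel. If not, the reported SE departs from the true one. Superiority rests on this one interval, so its width should be right for whatever pattern of losses occurs.

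**Working it through.** **The plan's own figures.** The documents give no SE for the device difference. The nearest figure is the power in Table 3. A paired t-test with SD of the difference √(2500 + 225) = 52.2 and a difference of 15 mL gives 59.1% power at 60 pairs, not 87.7%; the tabulated 87.7% appears at 120 pairs. That is a separate matter. Only the two SDs are used below.

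**Inputs.** SDs of 50 and 15 and correlation 0 (10.7); 72 randomised (10.7) in equal sequences of 36 (5.8). Assumed: 14 subjects (about 20% of 72) have Visit 2 data only, leaving 58 completers. The splits are also assumed, and are written as investigational-first/comparator-first.

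**Formulas at correlation 0.** At each visit v, with n_I and n_C values per device, let w_v = n_I·n_C/(n_I + n_C).
- Pooled variance: s² = (225·N_I + 2500·N_C)/(N_I + N_C), where N counts all values on a device.
- Model SE² = s²/Σw_v.
- True SE² = Σ w_v²(2500/n_C + 225/n_I)/(Σw_v)².
- Non-coverage = 2·P(Z > 1.96 × model SE/true SE).

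**Split 10/4.** Visit 2 has 36 and 36 values, so w = 18. Visit 3 has 26 comparator and 32 investigational values, so w = 26·32/58 = 14.345. The sum is 32.345.
- N_I = 68 and N_C = 62, so s² = (15,300 + 155,000)/130 = 1310.
- Model SE = √(1310/32.345) = 6.36.
- True SE² = [324 × 75.69 + 205.8 × 103.19]/1046.2 = 43.74, so the true SE is 6.61.
- Non-coverage = 2·P(Z > 1.886) = 5.9%.

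**All splits of 14:**

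| V2-only split | Model SE | True SE | Non-coverage |
|---|---|---|---|
| 7/7 | 6.47 | 6.47 | 5.0% |
| 10/4 | 6.36 | 6.61 | 5.9% |
| 12/2 | 6.31 | 6.72 | 6.6% |
| 14/0 | 6.26 | 6.84 | 7.3% |
| 4/10 | 6.61 | 6.36 | 4.2% |
| 2/12 | 6.72 | 6.31 | 3.7% |
| 0/14 | 6.85 | 6.27 | 3.2% |

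At correlations 0.2 and 0.4 the non-coverage changes by no more than 0.1 percentage point.

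**Losses that do no harm.** With 36 and 24 complete pairs and no Visit 2-only subjects, both SEs equal √[(2725/4)(1/36 + 1/24)] = 6.88.

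**Fewer Visit 2-only subjects.** With 7 instead of 14, and the other 65 complete, 5/2 gives about 5.4% and 7/0 about 6.0%. If the other 7 are lost before Visit 2 (58 completers), the figures are about 5.5% and 6.2%.

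**Simulation check.** With REML fits to normal data, 10,000 data sets per case and correlations 0 to 0.6, error rates were 5.0–5.4% at 7/7, 5.7–6.2% at 10/4, 4.0–4.3% at 4/10, 7.3–8.1% at 14/0 and 3.2–3.5% at 0/14. With equal SDs of 37 the two extreme splits gave 5.3–5.4%, so the unequal SDs are the cause.

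**How often.** If 14 losses fall at random, P(at least 10 investigational-first) = 0.09; in either direction it is 0.18. Averaged over all random splits, non-coverage is 5.0%.

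**After the fix.** With device-specific variances, treated as known, the reported SE is the true SE of that fit: 6.61 at 10/4, 6.36 at 4/10, 6.81 at 14/0 and 6.23 at 0/14.

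**The case against.** Several points on the other side stand.

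- **The plan is silent.** A reader might infer that 10.3 prescribes one residual variance. It does not. A model with a subject effect and residual variance grouped by device also fits its words. The gap is an unstated structure whose usual default conflicts with 10.7.
- **Uneven drop-out alone is harmless.** A reader might infer that any imbalance in losses spoils the SE. The 36/24 case shows otherwise; single-value subjects are needed. Section 10.7 does not say that discontinuation falls after Visit 2, and sections 6.3 and 10.7 allow replacement, which would dilute the share of such subjects.
- **No general inflation of type I error.** If drop-out is unrelated to device, the average error is 5.0%. The 18% probability counts both directions, and only about 9% is in the narrowing one. The documents give no ground for expecting device-dependent drop-out.
- **The SDs belong to the alternative.** They accompany means of 25 and 10 mL. If the devices had identical distributions, the SDs would be equal and the test would keep its level. The error rates here refer to CI coverage, or to equal means with unequal SDs.
- **A sensitivity analysis avoids the mechanism.** The Wilcoxon signed rank test uses pairs only. It does not correct the primary interval, however, and the per-protocol analysis repeats the same model.
- **Skewness may matter more.** Gamma-distributed data gave 9.1% error even at 7/7, and a variance structure does not cure that.

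**Conclusion.** The point holds as a minor one. Section 10.3 leaves the residual covariance open. The usual one-variance fit gives an interval about 4% too narrow at 10/4 and about 4% too wide at 4/10, and roughly 9% out in either direction if all 14 single-value subjects come from one sequence. Losses before Visit 2, complete pairs and an even split produce no error.

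This rests on SDs of 50 and 15 mL, normal data, and 14 (or 7) subjects with Visit 2 data only. The number and split of those subjects are assumptions. What is gained is a correct width for the split that actually occurs, and protection if drop-out should depend on device. Device-dependent drop-out could also bias the estimate, which a variance structure does not settle.

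**What to change.** In 10.3, keep visit and device as fixed effects and state the covariance. Use either an unstructured 2×2 matrix within subject, or a random subject effect with residual variance grouped by device. Index the matrix by device, not by visit, because each visit mixes the two devices. Name Kenward-Roger as the degrees-of-freedom method.

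The cost is one line of plan text and code, and one extra variance parameter (three instead of two). With complete pairs and sequences of equal size the device estimate is unchanged. With complete pairs in unequal sequences it shifts slightly, with a small gain in precision (SE 6.78 against 6.88 at 36/24, correlation 0).

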3.1 Objectives

Primary objective:

To demonstrate superiority of the new compact catheter in terms of improved bladder emptying, with the catheterisation performed by a health care professional.

Secondary objectives:

To assess safety and catheter perception of the new compact catheter.

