5.8 Randomisation Procedure

All subjects that have given informed consent and meet the inclusion and exclusion criteria will be randomised.

This investigation involves two treatments, the investigational device, and the comparator devices

The Rave RTSM™ is a validated randomization solution, that will be used for the randomization in this investigation. A centralized randomization will be implemented, in which, participants are to be randomly assigned to two intervention sequences in block sizes of 8.

For technical reasons, to ensure correct randomization in an equal split between treatment arms, the two treatment arms are technically implemented as illustrated below.

Treatment A: Investigational Device × Comparator 1 (SpeediCath Compact Eve) (25%)

Treatment B: Investigational Device × Comparator 2 (SpeediCath Compact Plus Female) (25%)

Treatment C: Comparator 1 (SpeediCath Compact Eve) × Investigational Device (25%)

Treatment D: Comparator 2 (SpeediCath Compact Plus Female) × Investigational Device (25%)

Randomisation will be 2:1:1 (Investigational device: Comparator: SpeediCath Compact Eve: SpeediCath Compact Plus Female)

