10.1 Statistical design, method, and analytical procedures

The primary objective will be evaluated by analysing the primary endpoint.

Baseline assessments and endpoints will be reported by descriptive statistics and/or listed.

Summaries will be presented by device i.e., investigational or comparator device and if relevant, by other grouping variables.

Descriptive statistics for continuous variables are presented with N, Mean, SD (standard deviation), Median, Min and Max, where N denotes the number of subjects contributing with non-missing data. For discrete variables, descriptive statistics are presented with N and percentage, where percentage is based on the total number of subjects/observations with non-missing data.

All statistical analysis will be performed with SAS version 9.4/Enterprise Guide version 7.1.

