10.4 Analysis of secondary endpoints

- Number of flow-stop episodes will be analysed, in a generalized liner mixed model (GLMM), with subjects included as a random component. Evidence of effect will be concluded, if the lower 95% confidence limit of the risk ratio between comparator and investigational device, is greater than 1.
- Average residual volume post catheterisation will be presented with Descriptive statistics for a continuous variable (N, Mean, SD (standard deviation), Median, Min and Max.)
- Adverse events will be listed and/or summarized.

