10.9 Pass/fail criteria

To demonstrate superiority of the investigational device, the null hypothesis of the primary endpoint must be rejected, at a 5% significance (alpha 0.05).

11 Data management

Data management and the final statistical analyses of all measurements described in this protocol are carried out by the Clinical Strategies team, Coloplast A/S.

Data will be collected through an electronic data capturing (EDC) system on electronic Case Report Form (eCRF), a secure, internet-based case report form. This system will be used to record all subject information collected in the investigation for secure data tracking and centralised data monitoring ("remote monitoring") done by monitors, as defined in the monitoring section.

The EDC system used is Rave EDC, version 2022.3.0, delivered by Medidata Solutions Inc. The system is designed to be compliant with the FDA requirements of 21 CFR part 11. It is a validated data management system allowing only qualified and trained personnel to enter the system. The system has full audit trail and electronic signature.

The data management system has restricted role-based access control. The principal investigator or delegate an CRA must be trained in the system prior to getting access. The sponsor will be responsible for training the principal investigator or delegate, in completion of the eCRF. The training is web-based and must be completed before access to the investigation is granted. Training will be documented in the data management system. The data manager will also demonstrate the system on a virtual meeting. Only the principal investigator, or delegate, will be authorised to enter data in the eCRF.

The monitor, using his/her personal login information shall verify all critical data points against the source documents and issue electronic queries for the authorised clinical site personnel to respond, as defined in the monitoring section.

A critical quality control will be performed by the sponsor's data management team and queries issued where needed. Such queries must be resolved by the site personnel.

The principal investigator, using his/her personal login information, shall sign each eCRF before the database can be locked. This must be done after acceptance from the data management team.

Automated, real-time access to the data enable control on study compliance and safety assessments.

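### Does the primary superiority rule in 10.3 let a result against the new catheter count as superiority?

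*Combined protocol and SAP*

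**What the plan says.** Section 10.3 analyses residual volume at first flow-stop in a linear mixed model with visit and device as fixed effects and subject as a random effect. Device has two levels, comparator and investigational. The decision rule reads: "Evidence of superior effect will be concluded, if the 95% confidence interval of the difference between comparator and investigational device, does not include zero".

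Three other places bear on how a pass is declared:

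- 10.8 fixes the level and the sidedness: "A significance level of alpha 0.05 (2-sided) will be applied". Its next sentence concerns the power to conclude superiority of the investigational device.
- 10.9 gives the pass/fail criterion: "To demonstrate superiority of the investigational device, the null hypothesis of the primary endpoint must be rejected, at a 5% significance (alpha 0.05".
- 10.4 states a direction for the number of flow-stops. Evidence of effect is concluded "if the lower 95% confidence limit of the risk ratio between comparator and investigational device, is greater than 1".

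The aim is set in 3.1: "To demonstrate superiority of the new compact catheter in terms of improved bladder emptying". Section 3.2 repeats it as a hypothesis of superior performance, and 10.7 assumes means of 25 mL (comparator) and 10 mL (new device).

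On the comparator, 5.8 says "This investigation involves two treatments, the investigational device, and the comparator devices", and 10.1 says "Summaries will be presented by device i.e., investigational or comparator device and if relevant, by other grouping variables".

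**The concern.** An interval can exclude zero on either side. Taking the difference as comparator minus investigational, an interval wholly below zero would mean that the new catheter leaves more urine behind at first flow-stop, yet it satisfies the wording of 10.3. Section 10.8 does not cure this, because a two-sided test rejects in both directions. Section 10.9 asks only that the null hypothesis be rejected. The secondary rule in 10.4 does name the bound that must be cleared, which makes the omission for the primary endpoint stand out.

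If the literal rule governed, the trial could declare success on evidence of harm, and the chance of a false superiority conclusion under no difference would be 5% instead of 2.5%.

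A related worry is that the two comparator products are pooled and no product-specific estimate is promised, so a pass does not show whether the benefit holds against each product.

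**Working it through.** **Inputs.** From 10.7: difference 15 mL, SD 50 mL (comparator) and 15 mL (new device), no within-subject correlation, 60 evaluable subjects. From 10.8: two-sided alpha 0.05.

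**SD of the within-subject difference.** With zero correlation it is √(50² + 15²) = √2725 = 52.2 mL.

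**The plan's own figure.** Table 3 gives 87.7% power for 60 subjects. A paired t-test with SD 52.2 mL and 59 degrees of freedom gives 59.1%. The four entries in Table 3 (71.9, 81.2, 87.7 and 92.2%) are matched to rounding with an SD of √(2725/2) = 36.9 mL and 2n − 2 degrees of freedom. With n − 1 degrees of freedom, the same SD gives 70.8, 80.4, 87.2 and 91.8%. That mismatch is a separate sample-size question. Both SDs are carried below so that nothing here depends on it.

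**Tails of the test.** SE = SD/√60, which is 6.74 mL or 4.77 mL. The non-centrality is δ/SE, and the critical value is t(0.975; 59) = 2.001. The literal rule is met in either tail; the directional reading counts only the favourable one.

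| True benefit δ of the new catheter | Favourable tail, SD 52.2 | Unfavourable tail, SD 52.2 | Favourable tail, SD 36.9 | Unfavourable tail, SD 36.9 |
|---|---|---|---|---|
| 0 mL | 2.5% | 2.5% | 2.5% | 2.5% |
| +15 mL (planned) | 59.1% | 0.0017% | 87.2% | below 0.0001% |
| −5 mL (assumed) | 0.36% | 10.9% | 0.14% | 17.7% |
| −15 mL (assumed) | 0.0017% | 59.1% | below 0.0001% | 87.2% |

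At the planned effect the two readings have the same power. They differ materially only when the new device is no better or is worse. To fall in the unfavourable tail, the observed mean would have to be worse with the new catheter by at least 2.001 × 6.74 = 13.5 mL, or 2.001 × 4.77 = 9.5 mL.

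**Could such a result be reported as a pass?** Reading the passages together:

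- 10.3 concludes a superior effect, not merely a difference.
- 10.8 and 10.9 both name the investigational device as the one whose superiority is at issue.
- 10.9 makes rejection of the null a requirement for that claim. It does not say that rejection alone is enough.
- 3.1 defines superiority as better emptying, which for this endpoint means a lower volume, and the means in 10.7 agree.

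A trial in which the new catheter left at least 9.5 mL more urine could not be described as having shown better emptying.

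**Product-specific estimates.** With about 30 subjects per comparator product, the SE is 52.2/√30 = 9.53 mL or 36.9/√30 = 6.74 mL. With t(0.975; 29) = 2.045, the 95% half-width is 19.5 or 13.8 mL, against a planned effect of 15 mL. Power at 15 mL is 33.1% or 57.6% per product.

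**The case for a change.** The strongest argument for a change is that a pass rule for the only confirmatory claim should be complete as written, without recourse to the objective. The sponsor already uses a directional form in 10.4, so one clause in 10.3, echoed in 10.9, would close the gap at no cost in power or subjects. All of that is accurate, and anyone revising the document for other reasons could add the clause.

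What does not stand is the suggested consequence. The 59% and 87% chances of a wrong-way pass need a device that is truly 15 mL worse, which the documents do not suggest, and a reader willing to call that outcome superiority against 3.1, 3.2, 10.8 and 10.9. The 5.0% against 2.5% contrast is simply the two tails of any two-sided test. Claiming superiority only in the favourable tail is the ordinary practice.

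On pooling, it is true that a pooled pass does not establish benefit against each product. But the plan declares a two-treatment comparison and makes no product-specific claim. Section 10.1 already allows summaries by other groupings, and estimates as imprecise as those above could flag only a large inconsistency. A committed table would be a preference, not the repair of a defect.

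**Conclusion.** The concern does not call for a change. Section 10.3 leaves out the sign, and the omission is real. However, the objective, the hypothesis, the planning means and the wording of 10.8 and 10.9 all point one way, and any competent analyst would fill the gap accordingly. Read that way, the chance of a false superiority conclusion under no difference is 2.5%, and power at 15 mL is 59.1% or 87.2%, identical to the literal rule to within 0.002 percentage points. The model, sample size and realistic conclusions are unaffected.

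This rests on a paired t approximation to the mixed model with 60 complete pairs, and on an SD of the difference of either 52.2 or 36.9 mL. The conclusion is the same for both. The pooled comparison is the declared one and needs no supplement.

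### The signed-rank sensitivity analysis of RV1 leaves out the visit effect that the primary model adjusts for, so its error rate is off if RV1 differs between visits 2 and 3

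*Combined protocol and SAP*

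**What the plan says.** Section 10.3 of the combined protocol and SAP states that RV1 "will be analysed in a linear mixed model (LMM) with subjects included as a random component". The fixed effects are device and "Visit (visit 2 and 3 of catheterisation"). The decision rule is: "Evidence of superior effect will be concluded, if the 95% confidence interval of the difference between comparator and investigational device, does not include zero".

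Under the sensitivity analyses in the same section, the second item reads: "Also, a Wilcoxon signed rank test will be applied the primary analysis, under the assumption of data not being normally distributed". Nothing is said about how visit or order enters that test, what happens to subjects with data from one visit only, whether an estimate accompanies it, or how a result that disagrees with the mixed model is to be read.

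On allocation, section 5.8 says "participants are to be randomly assigned to two intervention sequences in block sizes of 8". It lists four technical arms of 25% each, which makes device order 1:1. Section 10.7 sizes the trial "assuming a difference of 15 mL", with means (SDs) of 25 (50) and 10 (15) mL and no within-subject correlation. Section 10.8 adds: "A significance level of alpha 0.05 (2-sided) will be applied".

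**The concern.** In a two-period crossover, each subject's device difference also contains the visit difference, with opposite sign in the two orders. The primary model removes it and the signed-rank test does not. The plan therefore treats visit as worth adjusting for in one analysis and drops it from the analysis meant to check that one.

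The check is likely to be consulted. RV1 is a final volume minus an earlier volume on the same accumulating curve, so it is essentially bounded below by zero. A planned SD of twice the mean in the comparator arm (50 against 25 mL), and of 1.5 times the mean in the active arm (15 against 10 mL), implies strong right skew. At stake is how far readers can rely on the one analysis offered against non-normality, not the formal conclusion of the trial.

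**Working it through.** **The plan's own figures.** The plan gives no error rate or power for the signed-rank test. Its only power figure is 87.7% at 60 subjects (section 10.7, Table 3). From the stated inputs, the SD of a paired difference is √(50² + 15²) = 52.2 mL, and a two-sided paired t-test with 60 pairs has 59.1% power, so that figure does not reproduce. That is a separate matter. The comparison below sets two tests side by side on the same simulated data and does not rest on Table 3.

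**Where the visit effect goes.** Let δ be the comparator-minus-investigational difference and π the V3-minus-V2 shift.

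- Comparator minus investigational: δ + π for an investigational-first subject, δ − π for a comparator-first subject. With n₁ and n₂ completers in these orders, the average is δ + π(n₁ − n₂)/(n₁ + n₂).
- With π = 10 mL: at 30:30 the extra term is 0; at 33:27 it is 10 × 6/60 = 1 mL; at 36:24 it is 10 × 12/60 = 2 mL.
- At 30:30 the shift cancels on average but still widens the pooled differences, which makes the signed-rank test conservative.
- V2 minus V3: −δ − π for investigational-first, δ − π for comparator-first. The difference between orders is 2δ, and π drops out.

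**Type I error.** Simulation with 60 complete pairs, no within-subject correlation, identical devices, and nominal 5% two-sided tests. Gamma and lognormal shapes and the visit shift are assumptions.

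| Completers by order | Signed-rank | Rank-sum on V2 − V3 |
|---|---|---|
| 30:30, 10 mL shift | 0.6–3.6% | 4–5% |
| 33:27, shifts from 0 to 25 mL | 2.2–5.4% | 4.4–5.4% |
| 36:24, 10 mL shift | 6–10% | 4–5% |

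A repeat at 10 mL (10,000 trials per setting; gamma and lognormal, with mean/SD 25/50 or 10/15) gave 1.2–4.0% at 30:30 and 6.0–10.4% at 36:24 for signed-rank, and 4.8–5.5% for rank-sum. The excess at 36:24 lies almost wholly in one direction, set by the sign of the shift and by which order has more completers.

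**Power at the planned effect, 30:30.**

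- Lognormal, 10 mL shift: 81.7% for signed-rank, 89.1% for the visit-adjusted rank test.
- Lognormal, no shift: 88% and 87%.
- Gamma, no shift: 26% and 27%.
- Gamma, 10 mL shift (repeat run): 30% and 26%. The power loss is therefore shown for the lognormal shape, not for every shape.

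**How likely is 36:24?** Section 10.7 moves from 60 to 72 subjects, which allows 12 losses. Full blocks of 8 give 72/8 = 9 blocks and 36:36 at randomisation. A 36:24 split then needs all 12 losses in one order. If loss is unrelated to order, the probability is 2 × C(36,12)/C(72,12) ≈ 0.00016. A split of 33:27 or worse has probability about 0.11, and there the signed-rank error stayed near or below 5%.

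**The case against.** The strongest reply has four parts.

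1. *The test cannot alter the conclusion.* This stands. Section 10.3 rests superiority on the mixed-model interval, and section 10.9 requires only that "the null hypothesis of the primary endpoint must be rejected, at a 5% significance (alpha 0.05"). A reader might infer that the Wilcoxon test can replace the model or overturn its result; neither section provides for that.

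2. *False support for the device is remote.* This also stands. It needs both a material visit shift and a split near 36:24. Section 6.3 allows replacement of withdrawn subjects. Losses related to order, or exclusion of individual data points under section 10.2, could unbalance the completers, but the documents give no reason to expect it.

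3. *No visit effect is documented.* True. The 10 mL shift is assumed, and it is two thirds of the planned 15 mL device effect. Section 7.2 limits visit differences by requiring the same position at V3 as at V2 and a minimum bladder volume. Yet the primary model adjusts for visit anyway, and doing the same in the rank test costs nothing.

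4. *Not targeting the mean is normal for a rank test.* This stands too. One might infer that the signed-rank test is wrong because it can miss a real mean difference: with gamma data at the planned inputs, the mean comparison was significant and the signed-rank test was not in 41% of trials. With lognormal data this was 3%, and the documents do not give the distribution. The visit-adjusted rank test shares the property. With equal means of 25 mL and SDs of 50 and 15, signed-rank rejected in 57–60% of trials and the adjusted rank test in 54–57%; the signed-rank rejections all went against the new device. This calls for a sentence on interpretation and is not a defect of the signed-rank test in particular.

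**Conclusion.** The point holds as a specification gap in a sensitivity analysis. A plain signed-rank test drops the visit effect that the primary model contains. Under an assumed 10 mL visit shift it is conservative when completers are balanced between orders, and it loses about 7 percentage points of power in the lognormal case (89.1 − 81.7 = 7.4). It exceeds its nominal level only under an imbalance that the allocation scheme makes improbable. With no visit effect it behaves as well as the alternative.

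The sizes rest on assumed visit shifts and distribution shapes, 60 complete pairs and the plan's zero correlation. That the visit effect cancels in the V2-minus-V3 comparison between orders needs none of these; it assumes only that the shift is the same in both orders. The documents do not support saying that the trial's conclusion is at risk, or that the test is likely to lend false support to the device.

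**What to change.** In section 10.3, replace the signed-rank item with the following:

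- For each subject with RV1 at both visits, take V2 minus V3. Compare these differences between the investigational-first and comparator-first orders with a Wilcoxon rank-sum test, stratified by comparator product (van Elteren).
- Report a Hodges-Lehmann estimate with its confidence interval as half the between-order shift, comparator-first minus investigational-first, so that it reads as comparator minus investigational in mL.
- State that only subjects with both visits enter, and that the test addresses a location shift, not the mean difference in mL. With skewed data and unequal SDs it may therefore disagree with the mixed model. Say in advance how such a disagreement will be read.

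A permutation test of the mean V2-minus-V3 contrast may be added but should not replace the rank test. It largely repeats the mixed-model comparison (power 70% against 68% with gamma data, 87% against 81% with lognormal), and it would remove the outlier-resistant check. Nor is it exact for equal means with unequal SDs: at means of 25 mL and SDs of 50 and 15 it rejected in 8% (gamma) and 11% (lognormal) of trials.

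The cost is a few sentences in the plan and a few lines of code. The complete pairs are the same, and without a visit effect the change in power is about one percentage point either way.
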